## RESEARCH DESIGN AND METHODS

Briefly describe study design and anticipated enrollment, i.e., number of subjects to be enrolled by researchers study-wide and by Partners researchers. Provide a brief summary of the eligibility criteria (for example, age range, gender, medical condition). Include any local site restrictions, for example, “Enrollment at Partners will be limited to adults although the sponsor’s protocol is open to both children and adults.”

**Research Design:** The process of developing and validating a measurement instrument is iterative.

Figure 1 depicts the overall plan for creating a DS health instrument (DHI). The sequence of tasks is:

- Phase I: Development of conceptual model with well specified constructs (or dimensions)
- Phase II: Generation of an item pool of new and adaptation of existing items mapped to constructs
- Phase III: Cognitive evaluation of items (face/content validity)
- Phase IV: Reliability and validity analyses
- Phase V (Future): Responsiveness, evaluation of sensitivity to change, test in Spanish-speakers*

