Power calculation: Sample sizes are based on several criteria. The basic rule of thumb for psychometric analysis (primarily correlation analyses) is 10 subjects per survey item. The current conceptual model includes 95 items, with refining in SA1, I plan a final item pool of 70 items. The current target sample sizes will support up to 70 variables (items) available for inclusion in psychometric analyses. For instance, if the final instrument contains 70 items, 700 subjects are sufficient for 80% power to detect a difference of  $\geq .25$  standard deviations using type I error of 0.10.

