The primary aim of this research project will be to develop a survey instrument valid to measure health of individuals with Down syndrome ages 0-21 years. As such, the focus is on the psychometric properties of the survey instrument; the study outcomes are the psychometric assessments of the instrument.

Pre-determined Sample Size Calculation and Recruitment Goal

Sample size was determined *a priori* based on the sample size needed to conduct the psychometric analysis. The basic rule of thumb is that (5-10) ten subjects per item are needed for analyses.³⁹ For instance, if the final instrument contains 50 items, 500 subjects are sufficient for 80% power to detect a difference of $\geq .25$ standard deviations using type I error of 0.10. For our DHI with 113 core items, a sample size of 565-1130 caregivers is needed based on using an alpha of .05, a targeted power of .80, and an assumed change of 20% in the score between baseline and follow-up.

Determining “Complete” Surveys

We will closely follow progression through the components of our survey from screening to consent to survey. We considered a survey “Complete” if a participant had a timestamp for completing the DHI section. This occurred when individuals advanced from the final item in the DHI section. Although 683 individuals started the DHI section of our survey, 542 were completed and included in our study.

Item-level Evaluation

Item Distributions (including Missing data)

Ensure no “out of range values” including confirming branching logic followed flow to subsequent questions or skipped as we anticipated / planned.

Basic descriptive statistics are used to report distributions of continuous variables with mean, standard deviation, IQR and frequency for categorical variables. Item distributions evaluated missingness as well as floor and ceiling effects, defined at greater than 85% of responses located in item response anchor. For those with $\geq 85\%$ response at the tails, our research team reviewed the corresponding item and discussed if item should be eliminated. For example, we did not eliminate items related to developmental skills / milestones based on floor and ceiling effects as more than half of individuals are expected to attain some of these skills across the age span studied.

Handling of missing data

Item missingness was evaluated.

Survey-level Evaluation

Scale scoring for all scales/measures:

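### The final SAP attributes its 565-1130 sample size to alpha, power and a 20% change, but the figure is only 5-10 subjects per item for 113 items, and the 542 analysed fall below it without comment

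*SAP*

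**What the plan says.** The section of the final SAP on the pre-determined sample size and recruitment goal opens with a rule: "The basic rule of thumb is that (5-10) ten subjects per item are needed for analyses". It illustrates the rule with a power statement, that "if the final instrument contains 50 items, 500 subjects are sufficient for 80% power" for a difference of at least 0.25 SD at a type I error of 0.10. It then turns to the instrument as fielded, which has 113 core items, and states that "a sample size of 565-1130 caregivers is needed based on using an alpha of .05, a targeted power of .80". The effect size attached to that requirement is given as "an assumed change of 20% in the score between baseline and follow-up".

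The next section, on which surveys count as complete, reports: "Although 683 individuals started the DHI section of our survey, 542 were completed and included in our study".

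The protocol's power calculation, repeated in the original plan at the front of the SAP, uses a single value of 10 subjects per item and plans 70 items. There, "700 subjects are sufficient for 80% power to detect a difference of" at least 0.25 SD, again at a type I error of 0.10. The protocol's research design lists, as a later stage, "Phase V (Future): Responsiveness, evaluation of sensitivity to change".

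**The concern.** The wording presents 565-1130 as the result of a power calculation for a change in score over time. If it is not, the only sample-size justification in the final SAP gives a false basis for its number and ties it to a comparison that the study does not make. The same section calls at least 565 caregivers necessary, and the next reports 542 analysed without setting the two side by side. A reader judging whether the psychometric results rest on enough data needs to know which rule set the target, that the rule was relaxed, and how far the analysed sample fell from it.

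**Working it through.** **Inputs.** From the final SAP: 5-10 subjects per item, 113 core items, alpha 0.05 (sidedness not stated), power 0.80, a 20% change, 683 surveys started and 542 analysed. From the protocol and the original plan: 10 per item, 70 items, 700 subjects. The documents give no baseline mean, SD of change or test-retest correlation.

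**1. The stated figure, from the rule.** 5 x 113 = 565 and 10 x 113 = 1130. Both match exactly.

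**2. The stated figure, from alpha, power and a 20% change.** For a paired change, N = ((z_alpha + z_power) / d)^2, where d is the change divided by the SD of change. With two-sided alpha 0.05 and 80% power, (1.960 + 0.842)^2 = 7.85. The SD of change has to be assumed; here it is a multiple of the baseline mean, so d = 0.20 / multiple.

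| Assumed SD of change / baseline mean | N |
|---|---|
| 0.2 | 8 |
| 0.3 | 18 |
| 0.5 | 50 |
| 1.0 | 197 |
| 2.0 | 785 |

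Working backwards, N = 565 needs an SD of change 1.70 times the baseline mean, and N = 1130 needs 2.40 times (1.91 and 2.70 if one-sided). As standardised changes these are 0.118 and 0.083. If 20% is instead read as 0.20 SD, the paired N is 197 (155 one-sided) and a two-group total is 786 (620 one-sided). Two forms come near 1130: 786 / (1 - 0.30) = 1123 with an invented 30% dropout, and 1128 in total for proportions of 0.40 against 0.32. Both need inputs that the documents do not give, neither also yields 565, and the DHI score is continuous.

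**3. Whether a change endpoint exists.** The final SAP says that its outcomes are psychometric assessments. Responsiveness belongs to Phase V. The only repeat measurement is the retest, analysed for agreement, and an item screens out respondents whose status changed in a major way. An assumed 20% change does not fit an analysis meant for stable people.

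**4. The sample achieved.**
- Per item: 542 / 113 = 4.80.
- Against the lower bound: 565 - 542 = 23, and 23 / 565 = 4.1% short.
- Against the upper bound: 542 / 1130 = 48%.
- Against the original 700: 542 / 700 = 77%.
- Items supported by 542: 542 / 5 = 108 at five per item, 542 / 10 = 54 at ten.
- Completion: 542 / 683 = 79.4%. The starters would have met the lower bound (683 / 113 = 6.04), but the sample-size section makes no allowance for non-completion.

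**5. What the table of changes records.** Its power-calculation row gives the move from 70 to 113 items. It does not record the move from 10 to 5-10 per item. On the original rule, 113 items would call for 1130.

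**The case against.** The rule of thumb is stated openly in the same section, so an attentive reader can see where 565-1130 comes from. Both 565 and 542 are printed, and the SAP nowhere claims that the target was met. The shortfall is uncommented, not concealed. That all stands, and it limits the point to a wrong stated basis and a missing comparison.

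Several stronger readings are tempting, and the documents do not support them.

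- A reader might infer that the 500- and 700-subject examples are wrong. They say only that those numbers suffice for 80% power. At 0.25 SD and two-sided alpha 0.10, two equal groups need 2 x (1.645 + 0.842)^2 / 0.0625 = 197.8, so 198 each and 396 in total. With equal groups, 500 gives 87.5% power and 700 gives 95.2%, so both suffice. Even a 136/364 split of 500 gives 80.0%. The numbers come from 10 per item (10 x 50, 10 x 70), but the statements are not false on that reading.
- A reader might infer that no analysis could carry any 80% power statement. Mean comparisons do exist: between sampling frames in the original plan, between DS and ASD caregivers in the protocol, and paired t-tests at retest. The documents do not say which one the 0.25 SD refers to. Only the 20%-change clause lacks a matching endpoint.
- A reader might infer that the 113-item range was set after the data were in. The documents do not date it.
- A reader might infer that the factor analysis is underpowered. Exploratory analyses were run within three domains and low-loading items were dropped, so subjects per analysed item may well exceed 4.80. The item counts per domain are not given.

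**Conclusion.** The point holds. The 565-1130 range is the per-item rule and nothing else. The alpha, power and 20% change attached to it do not generate it, cannot be checked without an SD of change, and describe an endpoint that this study lacks. The analysed sample misses the SAP's own lower bound by 23 caregivers (4.1%), and neither that nor the relaxation of the rule is stated.

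The consequence is modest. Moving from 565 to 542 widens a standard error by about 2% (the square root of 565/542 is 1.021), and the miss does not by itself invalidate the factor analysis. This should be corrected because it is a relied-on statement that is wrong as written; it does not make the data unusable.

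The match in step 1 needs no assumption. The figures in step 2 depend on the assumed SD of change, which is why a range is shown.

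**What to change.** Delete the clause that ties 565-1130 to alpha, power and a 20% change, and replace it with text such as:

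> The original target was 10 per item x 70 planned items = 700. The fielded pool has 113 core items, for which the 5-10 per item rule gives 565-1130. 542 complete surveys were analysed (4.8 per item), below the lower bound.

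Add the move from 10 to 5-10 per item to the table of changes.

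Report the number of subjects, the number of items and their ratio for each factor analysis actually run. Give confidence intervals for the correlations with external measures, using the actual n for each measure. That n should not be taken as 542, because a survey counts as complete once the DHI section is finished, and the number completing each external measure is not stated.

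The cost is SAP wording plus counts and intervals from data already held. No new data collection or change of analysis method is needed. The stated position becomes slightly less favourable.

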**Focus Groups:** Individuals with DS and caregivers of individuals with DS will be recruited from the MGH DSP and the local Massachusetts DS Congress (MDSC) to participate in focus groups as well as patients who have previously consented in Database protocol (Protocol #:2012P000828) to be contacted about additional research studies (N=42). In Year 1, I will lead these groups in discussion of health using a modified think-aloud approach with structured and unstructured probing. Focus groups will be audio-recorded and transcribed. Focus group discussion will be used to identify emerging themes / topics (e.g. prioritize, identify components of health) which will be used to refine the conceptual model, refine existing items, and generate items for DHI. They will be used to develop items mapped to constructs, thereby increasing item pool. Then the item pool will be evaluated using cognitive interviews. Approximately twelve focus groups of approximately 6 participants will occur in the MGH DSP conference room or will be conducted virtually through the PARTNERS-approved secure version of Zoom platform. Focus groups will be grouped by age to attain homogeneity of the group; group composition can impact participants' comfort to say what they think or feel. The six groups will be enrolled with attention to factors such as age of child with DS, developmental level of child with DS, or other emerging factors. The rationale for the number of focus groups is to be able to have a focus group for each of the relevant age ranges cause you want homogeneity within groups, i.e., parents or caregivers whose kids may be dealing with same developmental issues.

[figure not shown]

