1. Develop the scoring algorithm, including minimum number of items requiring response to score. DHI scores are continuous and based on summed means of scale items with higher values indicating better health.
2. Evaluate scale score distributions; evaluate for floor and ceiling effects $\geq 10\%$ response at the tails.

Analysis of Key Psychometric Properties:

1. Factor Structure: principle components (PCA) and principle factor analysis (PFA) methods that included orthogonal (varimax) and oblique rotation (promax).^{39,40} Eigenvalue statistics are used to evaluate the strength of these relationships; a high eigenvalue indicates that an underlying subscale exists and low values indicate that the underlying subscale might not exist. If a subscale's eigenvalue meets the threshold for retention, the next step in the analysis is to evaluate how items relate to a particular factor using factor loading scores. We used standard criteria (eigenvalues > 1) and items within factors (factor loading scores > 0.40)^{39,40} in our iterative scale development process.

2. Internal Validity: Internal dimensional validity of scales was evaluated using factor analysis (FA). Initially, exploratory FA of item grouping within the 3 hypothesized domains (physical, mental, and social health) was conducted to identify factors within each domain, followed by a confirmatory FA of all items within those factors of all domains. The final factor loadings are a result of the confirmatory analysis. Internal consistency was evaluated with Cronbach's alpha. Items with factor loadings < 0.40 were dropped for low convergent validity; items with loadings > 0.9 were reviewed for redundancy and dropped as appropriate.

3. Test-retest Reliability: Reliability analyses included individuals who completed the retest survey. Test-retest reliability of each subscale score was assessed through the interclass correlation coefficient (ICC). An item was used to screen out individuals who experienced major changes in status between the test and the retest. Test-retest reliability was evaluated with paired t-tests and chi square tests at the item level and 2-way mixed-effects intraclass correlation coefficient (ICC) models at the scale level, with a 95% confidence interval of the estimate using the following guideline: poor (< 0.5), moderate ($0.5-0.75$), good ($0.75-0.9$), and excellent (> 0.90).

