4. External Criterion / Construct Validity: In the criterion validity evaluation, Pearson correlations served as the primary evaluation technique to evaluate how scores on our new measure correlated with scores on other external measures of components of health status (the PEDSQL, the SDQ, the CSHQ). Published scoring algorithms were used whenever available. General MOS items were scored using a simple mean.

We are seeking to establish validity to draw a valid inference about a distribution and establish some basic inferential validity. External validity will be operationalized using a multitrait-multimethod matrix (MTMM) approach, with the "gold standard" being establishment of forms of both convergent and divergent (discriminatory) validity.⁶² For validation of the DHI, each domain is considered a trait. Method refers to a measurement procedure, which includes consideration of both data source as well as data collection method. The referent method is a caregiver-administered survey. The data source is DHI respondent proxy-report for an individual with DS. The data collection methods include survey instruments and medical record review of clinically-significant metrics. Generally, correlation

coefficients between DHI domains and data external to the DHI will be used as evaluative criteria, with the specific correlation statistic being determined by the test value variable type. Utilization of the MTMM allows evaluation of correlation within and between methods and sources as well as within and between dimensions or traits.

Subgroup Analyses

We anticipated analysis by mode (PAPI vs CASI) but found that nearly all individuals elected to complete CASI.

All analyses were conducted using SAS® (v. 9.4).

All analyses were conducted using SAS, version 9.4 (SAS Institute, Cary, NC) and R, version 2.1.9 (R Core Team, Vienna, Austria), with R package psych. The protocol was registered ([ClinicalTrials.gov](https://clinicaltrials.gov/ct2/show/study/NCT04631237); NCT04631237).

This study was approved by the MGB Institutional Review Board. De-identified supporting data are available upon request from the authors.

Changes to Statistical Analysis Plan

Section	Original	Final
Power Calculation	Planned 70 items in final pool	113 core items in final pool
Determining Complete surveys	-	Added information regarding determination of “Complete” survey
Item-level evaluation	-	Added details regarding missingness and handling missing data

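### Age-dependent milestone items are pooled over ages 0-21 with no age adjustment described, so loadings, alpha and criterion correlations of milestone-heavy scales can reflect age rather than health

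*SAP*

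**What the plan says.** The final SAP (Planned Method of Analysis) aims for one instrument, "valid to measure health of individuals with Down syndrome ages 0-21 years".

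Under Item-level Evaluation, a floor or ceiling effect is "defined at greater than 85% of responses located in item response anchor", and flagged items go to team review. Milestone items were not removed on this ground: "we did not eliminate items related to developmental skills / milestones based on floor and ceiling effects as more than half" (the reason in full is that "more than half of individuals are expected to attain some of these skills across the age span studied").

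Under Survey-level Evaluation, "DHI scores are continuous and based on summed means of scale items with higher values indicating better health". No age norm or age-specific scoring is given.

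Under Analysis of Key Psychometric Properties, factors are sought within the physical, mental and social domains. They are kept on eigenvalues above 1, and items on loadings above 0.40. Internal consistency is Cronbach's alpha. For external criteria, "Pearson correlations served as the primary evaluation technique to evaluate how scores on our new measure correlated" with the PEDSQL, SDQ and CSHQ.

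None of these steps mentions age. The only subgroup analysis named is survey mode, and the table of changes adds no age analysis.

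**The concern.** A milestone item records whether a skill has been attained. Between birth and 21 years that is governed first by age. Two such items can be unrelated among children of the same age and still correlate strongly when infants and young adults are pooled. Factor analysis and alpha cannot tell that correlation from a common health construct.

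The rule that drops items loading below 0.40 does not protect against this, since a shared age gradient raises loadings. An age-driven score also brings age into every criterion correlation.

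The SAP states that the psychometric assessments are the study outcomes. Loadings, alpha and criterion correlations are therefore the results themselves, and a user of the instrument would read them as evidence that it measures health.

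**Working it through.** **Plan's own figures.** The plan gives no figure on this point. The nearest one reproduces (5 x 113 = 565 and 10 x 113 = 1130 caregivers) but does not bear on it. From the documents I take the age range, the retention rules (eigenvalue > 1, loading > 0.40) and n = 542 completed surveys. Age distribution, attainment ages and item counts per scale are not given, so everything below is an illustration on stated assumptions.

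**Model.** Ages are uniform on 0-22 unless stated. A yes/no milestone item with median attainment age a has P(attained) = 1/(1 + exp(-(age - a)/s)), with s in years. Items are independent given age and carry no health content. Alpha = k/(k-1) x (1 - sum of item variances / variance of the total). Age adjustment removes 1-year age-band means.

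**Step 1: six items, a = 2, 4, 6, 9, 12, 15, s = 1.5.**
- Pooled alpha 0.85; first eigenvalue 3.45 of 6; loadings 0.61-0.85; correlation of score with age 0.93.
- Age-adjusted alpha 0.02.
- Attainment is 89%, 81%, 73%, 59%, 45% and 32%, so only one item would reach the 85% rule.

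**Step 2: six items that all reach the 85% rule** (a from 0.5 to about 3 years, s = 0.5, 85-97% attained).
- Pooled alpha about 0.90-0.92; loadings 0.66 or higher; correlation of score with age 0.57-0.60.
- Age-adjusted alpha about 0.18-0.19.

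**Step 3: ten items, n = 542, 60 replicates per setting.** Ages are uniform or skewed young, a spans 1-4 or 1-10 years, and s is 0.5 or 1.5.
- Pooled alpha 0.87-0.95; first eigenvalue 4.6-7.2; essentially all loadings above 0.40; correlation with age 0.63-0.87; correlation with true health about 0.
- Age-adjusted alpha 0.03-0.25; 31-40% of loadings above 0.40.
- With a modest health effect on the milestones (0.5 logit per SD), pooled alpha is still 0.87-0.95 and age-adjusted alpha 0.17-0.36.

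Over steps 1-3, items without health content give alpha 0.85-0.95 pooled and 0.02-0.25 age-adjusted.

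**Step 4: criterion correlation through age alone.** If score S and external measure Y are linked only through age, r(S,Y) is approximately r(S,age) x r(Y,age). Assume r(Y,age) = 0.3.
- Step 1 items: 0.93 x 0.3 = 0.28.
- Step 2 items: 0.57 x 0.3 = 0.17 to 0.60 x 0.3 = 0.18.
- Step 3 items: 0.19-0.26 by simulation.
- Step 1 items plus 50 age-independent health items (loading 0.6, equal 0-1 scaling): 0.24 x 0.3 = 0.07.
- Step 1 items plus 107 such items (113 in all): 0.12 x 0.3 = 0.04.

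The two-sided 5% critical value at n = 542 is t/sqrt(540 + t^2) with t = 1.964, which is 0.084. The milestone-only values exceed it; the two mixed values do not.

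**Step 5: direction.** Take a score of ten milestone and ten health items, milestones without health content, and a criterion that correlates 0.6 with health.

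| Criterion's correlation with age | Pooled r |
|---|---|
| -0.3 | 0.01-0.12 |
| 0 | 0.25-0.31 |
| +0.3 | 0.44-0.49 |

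The age-adjusted r is 0.47-0.54. Here the pooled values range from slightly below it to almost nothing: age dilutes or masks a real relation.

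**The case against.** The case for the plan has real substance.

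- **Retention is documented only at the floor and ceiling screen.** The documents do not list the milestone items, say which survived the loading rule, or say whether they form their own subscale. This stands, and it limits any statement of size. A separate subscale would spare the other scales, but its own alpha, loadings and healthier-is-higher reading would still be open to the same problem.
- **Branching may route items by age.** The SAP mentions branching only as a check that respondents followed the planned flow. Age routing would reduce the problem, but it is not described.
- **The multitrait-multimethod approach also looks at divergent validity.** A shared age gradient should raise off-trait correlations there and might be noticed. That would neither identify age as the cause nor correct alpha and loadings.
- **Not deleting milestone items is defensible.** This stands. A reader might infer that the 85% rule should instead be applied within age bands. In narrow bands most milestone items are naturally near 0% or 100% (in step 1 the item with a = 4 is about 98% attained at age 10), so the rule would flag most of them mechanically.

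Two further inferences are tempting and unsupported. One is that a healthy 2-year-old necessarily scores below a sick 15-year-old. That depends on how milestone items are keyed and routed, which is not shown. The other is that convergent validity is inflated. Step 5 shows that the direction is not fixed, and the documents do not say how the PEDSQL, SDQ or CSHQ vary with age.

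**Conclusion.** The concern holds in conditional form. As written, the SAP's rules can certify a milestone-heavy scale as a coherent health scale when its items share only age. In the illustrations alpha is 0.85-0.95 pooled and 0.02-0.25 once age is removed, and the eigenvalue and loading rules are met throughout.

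The effect on criterion correlations depends on the scale and the measure. It is an inflation of about 0.17-0.28 for a milestone-only scale and a measure correlating 0.3 with age, about 0.04-0.07 for a score dominated by health items, and dilution or masking in other settings.

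All sizes rest on assumed ages, items and attainment curves. The documents do not show that the instrument's actual results are an artefact of age. They show that the described analysis could not tell.

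**What to change.** For every scale that contains a milestone item:

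1. Report alpha and loadings on age-residualised items, or fit a factor model with age as a covariate, beside the pooled results. Attainment is S-shaped in age, so use age bands or a smooth curve rather than a straight line.
2. Report age-partialled criterion correlations beside the unadjusted Pearson correlations.
3. Score milestone items relative to age, or as a separate developmental subscale, rather than as raw points towards better health.
4. State which milestone items remain, how they are keyed, and whether branching routes them by age. If age routing or age scoring already exists, saying so may settle much of the point.

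The cost is some extra analysis of data in hand; age is already needed to establish eligibility. Residualised items, a covariate model and partial correlations use all 542 surveys, so no small age strata are needed. The downside is that alpha and loadings may look less favourable.

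### Subscales are decided by eigenvalue > 1 without saying which eigenvalues; the rule can keep too many or too few factors, and parallel analysis should replace it

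*SAP*

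**What the plan says.** The final SAP, Analysis of Key Psychometric Properties, item 1 (Factor Structure), names "principle components (PCA) and principle factor analysis (PFA) methods that included orthogonal (varimax) and oblique rotation (promax") as its methods. It interprets eigenvalues as follows: "a high eigenvalue indicates that an underlying subscale exists and low values indicate that the underlying subscale might not exist". The operating rule is "We used standard criteria (eigenvalues > 1) and items within factors (factor loading scores > 0.40"). No other numeric criterion for retaining factors appears in the final plan.

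Item 2 (Internal Validity) says that exploratory factor analysis was run inside each of three hypothesized domains. A confirmatory analysis of the items in the resulting factors followed and supplied the final loadings. Items loading below 0.40 were dropped.

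The SAP's original plan (Internal Dimensional validity) also listed scree plots and a Kaiser-Meyer-Olkin (KMO) threshold of 0.70. Neither is in the final text. The change table does not record their removal; its survey-level row mentions only rotation.

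On size, the SAP says "For our DHI with 113 core items, a sample size of 565-1130 caregivers is needed" and "Although 683 individuals started the DHI section of our survey, 542 were completed and included in our study". The software is SAS and R, "with R package psych".

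**The concern.** The number and content of the subscales are what this study delivers, since the SAP defines its outcomes as the psychometric assessments of the instrument. An eigenvalue above 1 does not show that a subscale exists. In a finite sample of unrelated items, close to half of the PCA eigenvalues exceed 1 by chance. On the reduced matrix used by PFA the same threshold has no such meaning and can be too strict. A plan that lists both methods and leaves the choice open has not fixed its retention rule.

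The second cut-off has a related gap. The SAP does not state the correlation matrix. Its references to response anchors and chi-square tests imply that at least some items are categorical. Under Pearson correlations the loading of a skewed categorical item is pulled down by its distribution, and the 0.40 rule would then record it as lacking convergent validity.

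**Working it through.** **The plan's own figure.** 113 × 5 = 565 and 113 × 10 = 1130, so the stated range follows from the subjects-per-item rule alone. The analysed sample gives 542 / 113 = 4.8 per item, just under the lower end.

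**Inputs.** From the SAP: n = 542, 113 items, three domains, eigenvalue > 1, loading 0.40. Assumed, because the documents do not give them: 113 / 3 ≈ 38 items per domain, 3 or 5 true factors per domain, factor correlation 0.3, equal true loadings, and continuous items or binary items split 50–85%.

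**Number of factors kept.** I counted eigenvalues > 1 on the full correlation matrix (PCA) and on the matrix with squared multiple correlations on the diagonal (PFA). Parallel analysis compares the PCA eigenvalues with the 95th percentile from random data of the same size.

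| Truth (38 items, n = 542) | PCA > 1 | PFA > 1 | Parallel analysis |
|---|---|---|---|
| Pure noise | 18 | 0 | 0 |
| 3 factors, loading 0.5, continuous | 7.1 | 3.0 | 3.0 |
| 3 factors, loading 0.5, binary | 12.4 | 3.0 | 3.0 |
| 3 factors, loading 0.6, binary | 9.1 | 3.0 | 3.0 |
| 3 factors, loading 0.7, binary | 5.7 | 3.0 | 3.0 |
| 5 factors, loading 0.5, binary | 13.3 | 2.1 | 5.0 |

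With continuous items and 3 true factors, the PCA rule is nearly right at loading 0.6 (3.3) and right at 0.7 (3.0). The excess therefore comes from moderate loadings and coarse items. In the last row the two readings of the same rule differ by 13.3 / 2.1, about sixfold.

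**Do later steps repair the count?** In the 12.4-component case, after varimax rotation, 10.8 components still have at least two items above 0.40 and 6.1 have at least three. The confirmatory step is described with no separate sample and no fit criterion, so it cannot be relied on to remove surplus factors. It cannot restore factors that were never extracted.

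**The 0.40 cut, if Pearson correlations were used.** For a binary item with proportion p in one category, q = 1 − p, and threshold τ, the observed common-factor loading is λ·φ(τ)/√(pq).
- 85/15: φ(τ) = 0.233 and √(0.85 × 0.15) = 0.357, so the factor is 0.65. The latent loading needed is 0.40 / 0.653 = 0.61.
- 90/10: 0.175 / 0.300 = 0.58, so 0.40 / 0.585 = 0.68 is needed.
- 50/50: 0.399 / 0.500 = 0.80, so 0.50 is needed.

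If every item in the factor is split 85/15 in the same direction, the need falls slightly: the square root of the binary correlation is 0.388 at latent loading 0.55 and 0.404 at 0.57.

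In a one-factor simulation (10 items, 2 of them skewed) I took 5-point items with true loading 0.60. Their chance of falling under 0.40 on principal-axis loadings is 0%, 3%, 28%, 53% and 94% when 50%, 70%, 80%, 85% and 90% of responses sit in the top category. With 85% in one category, the chance is only 6–7% at a true loading of 0.70, and 3–9% at 0.60 if PCA loadings are used.

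**The case against.** The best defence is that the SAP lists PFA and calls the within-domain step exploratory factor analysis. If the threshold was applied to PFA eigenvalues, over-splitting largely disappears. That stands: over-splitting belongs to the PCA branch only. It does not rescue the rule, because on the PFA branch the rule can miss real factors.

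It is also fair that the items had been through expert panels, focus groups and cognitive interviews, so pure noise is a limiting case. A loading screen, Cronbach's alpha and a confirmatory step follow. Scree plots and KMO may still have been used, since the change table does not say they were dropped.

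A reader might infer several stronger things that the documents do not support:
- That about 51 spurious factors arise. This is the noise count for all 113 items analysed together by PCA, whereas the exploratory step was run within domains.
- That Pearson correlations were used for the factor analysis. They are named only for external criterion validity.
- That all 113 items are categorical. Response formats are not given.
- That the instrument both over-splits its domains and discards valid items. The two harms belong mainly to different methods: PCA gives many factors and few dropped items, and common-factor loadings drop more skewed items.
- That the 0.40 cut mainly measures prevalence. The effect is small at true loadings of 0.7 unless about 90% or more of responses share one category, and items with 85% or more at a tail were separately reviewed.

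**Conclusion.** The point holds as a fault in the stated retention rule. It does not show that the reported subscales are wrong. At the analysed sample size, eigenvalue > 1 on PCA keeps about 7 to 12 factors for 3 real ones at loading 0.5, and about 6 at loading 0.7 with binary items. On PFA it keeps the right 3, but about 2 of 5 with binary items at loading 0.5. Parallel analysis on PCA eigenvalues gives the true number in each of these settings. The counts rest on the assumed domain size, factor numbers, factor correlation and item formats.

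The concern about skewed items is conditional on Pearson correlations combined with common-factor loadings. Under those conditions it matters for items of moderate validity (true loadings of about 0.5 to 0.6) with roughly 80% or more of responses in one category.

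**What to change.** 1. State which correlation matrix was analysed, which eigenvalues the threshold was applied to, and whether the scree plots and KMO were kept.
2. Replace eigenvalue > 1 by parallel analysis within each domain (95th percentile of random-data eigenvalues), with the scree plot as a check. Say which eigenvalues are compared. In the 38-item simulations (which also included skewed 5-point items), the comparison on PCA eigenvalues kept 3.0 of 3 and 5.0 of 5 factors; on reduced-matrix eigenvalues it kept 3.0–3.4 and 5.0–5.8.
3. With that number of factors, base item retention and the 0.40 cut on the PFA solution with the promax rotation the SAP already lists.
4. As a sensitivity analysis, repeat with a polychoric matrix, collapsing sparse response categories where needed, and report which subscales and items change.

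The cost is a little more analysis on existing data, using an R package the SAP already names. The real price is that the reported subscale structure may change.
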